2.2 BACKGROUND

The etiology of ECC is multifactorial. Low socio-economic status is an ECC risk factor,⁵ but most ECC risk factors involve health behaviors,² such as high frequency of sugar consumption, especially from added-sugar beverages and juice,^{6,7} poor oral hygiene,⁸⁻¹³ and early MS colonization which children acquire from their mothers.¹⁴⁻¹⁷ Caries rates of 35% to 56% have been reported for WIC-enrolled children under the age of three years.¹⁸ Nearly 34% of all 2- to 5-year-old children living under the federal poverty level are affected by caries in the United States, with higher rates among minority children.¹⁹ Behavior-based risk factors (e.g., habitual sugar intake) place children at high risk for ECC. These risk factors are preventable, but the educational preventive messages that have been implemented for pregnant women and mothers have not been effective in increasing mothers' oral-care behaviors or in decreasing their young children's plaque, gingivitis or caries including some that have used videotaped messages.^{20,21}

This protocol tests the theory- and evidence-based motivational approach presented in the figure above. This approach and its behavioral strategies come from SDT.^{22,23} SDT is relatively unique among theories of motivation due to its focus on the quality, rather than the quantity, of motivation. Central to SDT is the distinction between self-determined or autonomous (i.e., high-quality) and non-self-determined or controlled (i.e., low-quality) forms of motivation.^{23,24} Types of motivation differ from one another based on the degree to which actions are (or are not) fully self-endorsed by the individual. Autonomous motivation reflects freely chosen and fully or whole-heartedly self-endorsed reasons for engaging in a behavior, such as "I want to do this because it is important and very useful to me".²⁵ In contrast, controlled motivation reflects reasons for acting that are not self-endorsed and carry little personal ownership because one feels pressured into doing them, such as "This is something I should do, even though I don't really want to" (internal pressure) or "This is something I have to do; it is required" (environmental pressure).²³

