- Prior to watching the videotaped messages at visits 1, 2 and 3, participating women from both groups will complete a series of pre-intervention questionnaires regarding their own oral health and their (future) child's oral health. The questionnaires will include information regarding the mother's (1) demographics; (2) perceptions and status of their own oral health; and (3) pre-intervention self-reported knowledge and behavior concerning their own oral health (dietary/oral hygiene behaviors, frequency of visits to the dentist, etc.), as well as concerning their child's oral health (child's dietary/oral hygiene habits, etc.).
- Immediately after viewing the videotaped oral health messages at visits 1, 2 and 3, participating women from both groups will complete two additional questionnaires to assess their perceptions of the degree of autonomy support of the videotaped messages. One questionnaire will assess the mothers' perceived feelings of autonomy, relatedness, and competence ("health care climate questionnaire"), and the other will assess the mother's internalization of the videotaped message (i.e., the degree to which mothers understood, agreed with, and perceived the oral health message as helpful and useful to them ["internalization questionnaire"]).
- SDT proposes that, if the participating woman has internalized the message, the changes should be evident within a short period of time.⁷ Thus, participating women from both groups will be asked to complete post-intervention questionnaires at *one-month follow-up* after viewing the videotaped messages at visits 1, 2 and 3 designed to assess mothers' changes in self-reported knowledge and subsequent oral health behavior towards their child's oral health. According to the informed consent approved by the UI IRB, "You (study participant) may feel uncomfortable in answering certain questions and you can choose to decline any aspect of the study at any time. You and your child may discontinue participating at any time without any negative consequences." Therefore, participants may choose not to complete the one-month follow-up questionnaires.

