9.2 SAMPLE SIZE DETERMINATION

Based on a sample size of 317, we should be able to entertain up to 31 covariates in a multiple regression model without jeopardizing model validity through overfitting (we note that this far exceeds the number of covariates targeted in this application, even allowing for reasonable examination of first-order interactions); this number would be smaller for logistic modeling, depending upon the distribution of the outcome variable. Finally, we note that modeling of outcomes such as clinical status and behavioral change can include covariates such as knowledge, behavioral intent, autonomy, competence, and relatedness. Such models incorporate the key aspects of the SDT intervention, can assist in the evaluation of the impact of SDT, and can offer validation of its application. The rich data set will permit formal evaluation of the validity of the theoretical basis of the proposed intervention, e.g., by evaluation of timing of behavioral change and whether it persists as prescribed by SDT, by assessing the relationships between outcomes and ratings of autonomy, competence and relatedness, and more systematically by use of mediation models.⁵⁸⁻⁶² While every effort will be made to maximize retention as outlined below, missing data issues will be addressed via multiple imputation^{63,64} the importance and utility of this approach have been substantiated for intervention trials targeting early childhood caries.⁶⁵ We will follow the general recommendations of Rubin^{66,67} and emulate the more specific aspects of execution of the caries-oriented analysis applied to these reported caries intervention trial data.⁶⁵ The possibility of selective dropout between the two groups will be fully explored, as will characteristics associated with dropout; sensitivity analyses will be conducted to explore the potential impact on results.

Power and Sample Size Considerations: Estimation of Detectable Effect Sizes

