For purposes of sample size calculation, the primary outcomes of interest are caries status as measured by the d_{1-2-3} mfs and d_{2-3} mfs indices at the third-year follow-up, i.e., at approximately three years of age; caries status at two-year follow-up represents a secondary outcome. Indices are derived from the modified d_1d_{2-3} mfs caries criteria. Required sample sizes are primarily based upon the experiences reported by Wagner et al,⁶⁸ which were felt to provide the most appropriate estimates of effect sizes and variability after translation from the WHO caries criteria. Therefore, assuming an effect size (treatment difference) of 1.1 (standard deviation 3.45) for the number of cavitated, missing or filled lesions, Type I error level of 0.05, and 80% power, required sample size is 156 children per group at the three-year follow-up. Given enrollment of 317 mother-child dyads for each group (experimental (SDT) video or neutral control), and a conservative annual attrition rate of 21%, 156 dyads per group (312 total) would be expected to

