9.4.2 ANALYSIS OF THE PRIMARY ENDPOINT(S)

Primary efficacy

The primary outcome is caries status, measured by the d_1d_{2-3} caries criteria for scoring dental caries in children developed by members of the Iowa Fluoride Study. Caries status as total counts of dmf surfaces will be calculated during yearly dental exams. These counts will be reported as means, medians, quartiles, standard deviations, and ranges for each intervention group. Data will be explored longitudinally using dmf surfaces at each age and dmf increments between ages. Analysis of caries outcomes will focus on Poisson and/or negative binomial modeling, possibly with variance inflation and zero inflation accommodation, as appropriate. To account for repeated longitudinal measurements, generalized estimating equations (GEEs) will be used to model these counts. A first-order autoregressive or AR(1) working correlation structure will be

assumed. The quasi-likelihood information criteria (QIC) will be used to compare models to select the best fit. The model will include age, gender, location (urban/rural), race, intervention, and mothers' knowledge and behavior. These are all clinically important known covariates that are associated with caries status, and mothers' intervention and behavior/knowledge are covariates of interest. These are planned covariates to include; however, if the number of covariates is limited by the sample size or infrequent observations of caries, we will use bivariate analyses to inform a more parsimonious final model. Results for the model will be presented as incidence rate ratios with 95% confidence intervals. Data will be analyzed on an intention-to-treat basis with sensitivity analyses considering the per-protocol dataset. Missing data will be addressed via multiple imputation and sensitivity analyses will be conducted to explore potential impacts on results.

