9.4.7 SUB-GROUP ANALYSES

To determine whether the effect of the assigned intervention is consistent across subgroups, similar models for both primary and secondary endpoints will be fit and estimated including but not limited to the following:

- Mother education level
- First time mother or not
- Mother income
- Mother race
- Mother oral health status
- Mother age (< 25 vs. 25 or older)

No subgroup analysis by sex will be performed, as only pregnant individuals will be enrolled in the study.

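### The primary caries model omits maternal education and maternal oral-health status, which the trial holds at Visit 1 and uses only for subgroups; a modest possible gain in precision is forgone

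*Protocol*

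**What the plan says.** **Covariates.** Protocol 9.4.2 states that "The model will include age, gender, location (urban/rural), race, intervention" and then adds mothers' knowledge and behavior. It justifies the list by the known association of these factors with caries. It also allows a shorter list, guided by bivariate analyses, if sample size or infrequent caries requires it. Section 9.4.3 reuses the list for the secondary endpoints, limited to one covariate per 10 observations or events.

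**The omitted factors.** Section 9.4.7 names maternal education and "Mother oral health status" as subgroup factors and gives them no other analysis role. According to 6.1.2, the questionnaires completed before the video cover demographics and mothers' "perceptions and status of their own oral health". The schedule in 1.3 places the mother's demographic questionnaire at Visit 1. Education is not itemized there, but the 9.4.7 subgroup needs it.

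**Relevance to caries.** Section 2.2 counts low socio-economic status among the risk factors and also lists "early MS colonization which children acquire from their mothers". Section 6.1.2 has the videos cover how the mother's oral health bears on the child's.

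**Room in the model and sample size.** Section 9.2 says the sample can carry "up to 31 covariates in a multiple regression model", and fewer in logistic models. It also states: "Type I error level of 0.05, and 80% power, required sample size is 156 children per group at the three-year follow-up". That calculation uses a difference of 1.1 and an SD of 3.45, with no covariate term.

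**The concern.** By the test that 9.4.2 sets for its own list, association with caries, the background text gives both omitted factors a claim to be included, and no reason for leaving them out is stated. A baseline factor that predicts the outcome sharpens the comparison between arms, and here the data are already collected.

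Missing data add to this. About half the children are expected at 36 months (156 of 317 per group, 49%), and 9.2 and 9.4.2 rely on multiple imputation. Education and maternal oral health could plausibly relate to both dropout and caries, so using them would make the assumption behind the imputation more credible.

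**Working it through.** **Step 1: the plan's own figure.** Inputs from 9.2: difference 1.1, SD 3.45, alpha 0.05 (taken as two-sided), power 80%.

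n per group = 2 × (1.960 + 0.842)² × 3.45² / 1.1² = 2 × 7.849 × 11.9025 / 1.21 = 154.4, so 155. The t-test version gives 155.4, so 156, as stated. A one-sided test gives 122 and does not match.

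Retention: 317 × 0.79³ = 156.3. Power at 156 per group is 80.4%. For the index with white spots (difference 1.7, SD 4.35) it is 93.2% against the stated 93%. All figures reproduce without covariate adjustment.

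**Step 2: a simple linear guide.** If the added covariates explain an extra share R² of the variance, the residual SD is 3.45 × √(1 − R²). R² is an assumption; the protocol gives none.

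| Assumed extra R² | Power at 156 per group | Completers per group for 80% |
|---|---|---|
| 0 | 80.4% | 155 |
| 0.01 | 80.8% | 153 |
| 0.05 | 82.4% | 147 |
| 0.10 | 84.3% | 139 |
| 0.20 | 88.3% | 124 |

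At R² = 0.05 the saving is 155 − 147 = 8 completers per group, or 8 / 0.79³ ≈ 16 enrolled dyads per group.

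**Step 3: closer to the planned count model.** Assumptions: 156 per group, difference 1.1, SD 3.45, negative binomial counts, a maternal factor present in 40%, robust standard errors, 3,000 trials per setting. Two independent sets of runs gave these powers, unadjusted to adjusted:

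| Control mean | Factor × 1.5, set A | Factor × 1.5, set B | Factor × 2, set A | Factor × 2, set B |
|---|---|---|---|---|
| 2 | 87.7 to 88.6 | 88.5 to 89.6 | 88.6 to 91.4 | 87.8 to 90.8 |
| 3 | 82.2 to 84.2 | 84.3 to 85.9 | 83.6 to 88.8 | 83.8 to 87.4 |
| 4 | 81.0 to 83.1 | 83.1 to 84.5 | 82.2 to 88.0 | 82.2 to 88.3 |

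The gains are 0.9 to 2.1 points at × 1.5 and 2.8 to 6.1 points at × 2. With no effect of the factor, power changed by at most 0.3 points. The Monte Carlo standard error of one estimate is about √(0.85 × 0.15 / 3000) = 0.65 points, so the smallest gains are not far from noise. Starting power differs from 80.4% because this is a count model and not a comparison of means; the change is what to read.

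**Step 4: overlap with listed covariates.** Step 3 compares an unadjusted model with one adjusted for a single factor, whereas the planned model already carries several covariates. Once runs with a correlated covariate already in the model are included, the range is about 0 to 2 points at × 1.5 and about 0 to 6 points at × 2, with no material loss if the factor is not prognostic.

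**Step 5: timing of the measurement.** Section 4.1 randomizes after consent, and the procedures table in 6.1.2 lists randomization before the pre-intervention questionnaires. The Visit 1 values are therefore post-randomization but pre-video. Mothers are to be blinded (6.3), so the values can still serve as baseline.

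**The case against.** The strongest reply is that the choice of prognostic covariates is discretionary. The omission contradicts nothing and makes no stated figure wrong. That stands, and it limits this point to an improvement.

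The premise is also thin. Socio-economic status is named as a risk factor in general, but every participant is WIC-enrolled and no gradient within that group is given. Maternal oral health is measured by questionnaire, and only the children are swabbed. No strength of association is documented. This stands, and it is why the result is a range that starts at zero.

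A reader might infer several stronger things that the documents do not support:

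- *The trial loses planned power.* It does not; the 80% takes no credit for covariates.
- *Adding covariates is free because 31 can be carried.* That figure is for multiple regression on 317, and 9.2 says it is lower for logistic models. Section 9.4.2 foresees trimming the list, and 9.4.3 imposes the limit of 10 per covariate.
- *The factors are measured before randomization.* They are measured before the video only.
- *The imputation leaves them out.* The protocol neither lists nor excludes imputation variables, and 9.2 promises to examine characteristics associated with dropout.
- *The effect measure keeps its meaning everywhere.* A rate ratio for count means does so under a log link. The odds ratios of the behavior models do not, and zero inflation is left open for the counts.

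Finally, the same sentence of 9.4.2 raises larger questions. It adjusts for knowledge and behavior, which the secondary objectives treat as mediators, without limiting them to baseline values. It also does not name the stratification factors, language and site. Adding two covariates repairs neither, but the point made here stands apart from them.

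**Conclusion.** The point holds in a limited form. Two baseline factors that the protocol itself treats as relevant to child caries, and uses for subgroups, are left out of the primary model without a reason. The stated sample size and power are sound on their own terms.

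The forgone gain is about 0 to 2 points of power if the factor multiplies caries by 1.5, and about 0 to 6 points if it doubles it. This rests on assumed values: 40% prevalence, control means of 2 to 4 surfaces and negative binomial counts. It shrinks with overlap with listed covariates and is nil if the factors are not prognostic. Education was not simulated separately. The benefit for the imputation is plausible but was not quantified.

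**What to change.** In 9.4.2, add the Visit 1 pre-video values of maternal oral-health status and maternal education as prespecified baseline covariates of the primary caries count model. State that they are retained whatever the bivariate screen shows, describe them as measured after randomization but before the intervention, and include them in that model's multiple imputation.

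In 9.4.3, add them only where the limit of 10 observations or events per covariate allows, and note that odds ratios from the logistic behavior models change meaning with adjustment.

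The cost is protocol and analysis-plan wording and a few extra parameters, with no new data. The extra parameters are a drawback only if caries proves very infrequent.

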9.4.3 ANALYSIS OF THE SECONDARY ENDPOINT(S)

Secondary efficacy

Secondary outcomes of interest include changes in knowledge and oral health behaviors of mothers, as well as plaque and microbial outcomes in children. Knowledge outcomes will be measured pre and post intervention via the score on the knowledge assessment. These measures will be considered as counts. GEE modeling will be used with Poisson or negative binomial distributions considered. Results will be presented as incidence rate ratios and 95% confidence intervals.

Maternal change in behavior will be assessed via a set of behavioral questions asked at multiple time points. Each individual question will be dichotomized into improved vs. did not improve based on the answers given pre and post intervention. When analyzing single time points, logistic modeling will be used. To evaluate behavioral changes over time, GEE models with a logit link function will be used. Results will be presented as odds ratios and 95% confidence intervals.

Visible plaque will be analyzed as the number of maxillary and mandibular incisors and molars with plaque at each visit. Analysis of plaque outcomes will focus on Poisson and/or negative binomial modeling, possibly with variance inflation and zero inflation accommodation, as appropriate. To account for repeated longitudinal measurements, GEE will be used to model these counts. Results will be presented as incidence rate ratios and 95% confidence intervals.

Levels of salivary MS will be reported as numbers of bacteria from each visit. Log transformation will be considered if data is skewed, and GEE models assuming a normal distribution with an identity link will be used when analyzing multiple time points. Results will be presented as adjusted least squares means estimates and 95% confidence intervals.

The same covariates as the primary endpoint will be used for both bivariate and multivariable modeling, subject to the constraint of 10 observations/events for every covariate included. Missing data may be addressed via multiple imputation. An AR(1) correlation structure will be assumed for all longitudinal models. QIC will be used for all model/covariate selection involving GEEs; AIC will be used for models calculated for single time points. Mediation analyses will proceed via Baron and Kenny's⁷⁴ steps for mediation analysis and significance will be calculated via Sobel tests.

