1.3 SCHEDULE OF ACTIVITIES

Study time-points and corresponding activities for ALL	Visit 1 Prenatal				Visit 2 Age 1 to 2			Visit 3 Age 2 to 3			Visit 4 Age 3+		
study participants in the experimental and control groups	Visit 1 at WIC	1-Month Follow-up	3-Month	9-Month Follow-up	Visit 2 at WIC	l -Month Follow-un	3-Month	9-Month Follow-up	Visit 3 at WIC	l -Month Follow-up	3-Month	9-Month Follow-up	Visit 4 at WIC
Informed Consent	\checkmark												
Group randomization	\checkmark												
Mother demographic questionnaire	~												
Mother knowledge questionnaire	~	✓		~	✓	~		~	✓	✓		~	✓
Mother behavior questionnaire	~	✓		~									
Intervention videotaped oral health message	~				~				✓				
Internalization questionnaire	~				~				~				
Health care climate questionnaire (HCCQ)	~				~				~				
Booster videotaped oral health message			~				✓				~		
Child plaque sample					\checkmark				\checkmark				✓
Child dental exam: plaque, caries and tooth status recordings					✓				~				✓
Child behavior questionnaire				~	✓	~		~	✓	~		~	~
Mother & child demographic questionnaire					~				~				✓
Mother behavior intent questionnaire													✓

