(2b) To test the degree to which the intervention produces its effects on children's oral health status through its mediating effects on mothers' changes in behaviors concerning their child's oral health (i.e., oral hygiene habits, dietary habits, use of fluoride, visits to the dentist, lift-the- lip to check for early signs of cavities)	behaviors toward the child's oral health will be assessed through a series of questions (i.e., visit to the dentist, detailed dietary and oral hygiene habits, etc.)	(2b) The same questionnaires were used and validated in several previous research projects from the research team. ^{10-13,50-} ⁵⁵	(2b) According to SDT, the greater the extent to which the autonomy- supportive message allows mothers to experience autonomy support and volitional internalization, the more positive will be the mothers' post-message oral health care motivation (need satisfaction, autonomous motivation), behavioral care for their children . In other words, mothers of high-risk children who receive our videotaped autonomy- supportive messages, compared to mothers of high-risk children who receive only videotaped neutral messages, will demonstrate more positive changes

OBJECTIVES	ENDPOINTS	JUSTIFICATION FOR ENDPOINTS	PUTATIVE MECHANISMS OF ACTION
	and nine-month follow-ups. *At the final visit (Visit 4), behavior questions will assess the key topics discussed previously at all three time points.		regarding behaviors towards their children's oral health, such as more positive oral hygiene and dietary habits, use of fluoride, visits to the dentist, lift-the-lip to check for early signs of cavities, etc.

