4 STUDY DESIGN

4.1 OVERALL DESIGN

This UH3 clinical trial study constitutes a Stage II research according to the NIH Stage Model.⁴ The study design specifies a two-arm, randomized controlled clinical trial to assess the effectiveness of autonomy-supportive videotaped oral health messages informed by SDT as a means of preventing ECC, as compared to the effects of exposure to neutral messages also delivered via videotape. The intervention is intended for use in public health settings attended by high-caries risk groups, and the proposed UH3 clinical trial will be conducted at several WIC clinic sites in different rural and urban counties in Iowa with relatively large Hispanic and African-American populations.^{51,52}

The study sample will consist of 634 pregnant women whose future children will be followed until they are 36 months of age. Pregnant women, between 12 and 36 weeks of the gestational period, 18 to 45 years old, and with no intention to move away in the next four years will be eligible to participate in the study. Recruitment will occur anywhere between 12 to 36 weeks of gestation. However, study interventions will only start between 16 to 36 weeks of gestation. If a pregnant woman is recruited between 16 to 36 weeks of gestation, the study procedures can begin immediately. If the woman is recruited between 12 to 15 weeks of gestation, we will schedule her an initial study visit for later, that is between 16 to 36 weeks of the gestation period. At their first study visit, informed consent will be obtained. After informed consent, they will be randomly assigned to one of two study groups: Group 1 (experimental (SDT) group) and Group 2 (neutral control group). The primary outcome of interest will be children's caries status. Secondary outcomes will be changes in children's oral health behaviors conducive to better oral hygiene and dietary habits, as well as lower levels of dental plaque and MS.

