The central hypothesis is that a theory-based intervention approach using videotaped messages and targeted to mothers of high-risk young children will promote an elevated sense of perceived autonomy, competence, and relatedness, which will in turn lead mothers to experience and demonstrate improved self-reported knowledge, behavioral intention and subsequent behavior concerning their child's oral health. Consequently, their child will have more positive oral health outcomes, such as lower levels of caries, dental plaque, and MS. We predict that the theory-based intervention will enhance mothers' oral health care knowledge (Hypothesis 1) and behavior toward their oral health and their child's oral health (Hypothesis 2), relative to neutral messages, also delivered via videotapes. In addition, these hypothesized benefits will apply to both short-term (one-month) and long-term (nine-month) effects across each time point (prenatal, Age 1-2, Age 2-3, Age 3+).

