Enrollment may take as long 18 months. Study participation will last approximately 42 months. We intent to enroll 317 pregnant mothers for each group: Group 1 (experimental - SDT)/Group 2 (neutral control). There will be four visits at the WIC clinics with three follow-ups after each WIC site visit. Outcomes will be measured at each study time points. Data will be collected in person at the WIC site visits and through completion of questionnaires through REDCapTM at follow-ups after each WIC visit. Visit 2, 3 and 4 will be scheduled based upon the child's DOB and will take place when the child is approximately 12, 24 and 36 months of age. Children will be examined (visits 2, 3 and 4) for visible plaque and dental caries by one of the study examiners who will be blinded to the participant's group allocation. Plaque samples will also be obtained from all participating children at visits 2, 3 and 4. Numbers of MS will be derived for each sample through the standard matrix counting methodology of the spiral plating system.

Detailed Description of the Study Procedures

The table below details the study procedures:

Visit	Time	Window	Purpose and Activities	Location
1.0	Visit 1	Day 0	Enrollment, informed consent, group randomization, pre-intervention questionnaires, video 1 message, post- video HCCQ and Internalization questionnaires	WIC Clinic
1.1	1 month	+8 weeks	Post-intervention questionnaires	Links via REDCap™
1.2	3 months	+6 months	Booster video 1 message	Links via REDCap™
1.3	9 months	+8 weeks	Post-intervention questionnaires	Links via REDCap™
2.0	Visit 2	1 year + 2 months	Pre-intervention questionnaires, video 2 message, post-video HCCQ and Internalization questionnaires, child's dental exam and plaque sample	WIC Clinic
2.1	1 year & 1 month	+8 weeks	Post-intervention questionnaires	Links via REDCap™
2.2	1 year & 3 months	+6 months	Booster video 2 message	Links via REDCap™
2.3	1 year & 9 months	+8 weeks	Post-intervention questionnaires	Links via REDCap™
3.0	Visit 3	2 years ± 2 months	Pre-intervention questionnaire data, video 3 message, post-video HCCQ and Internalization questionnaires, child's dental exam and plaque sample	WIC Clinic
3.1	2 years & 1 month	+8 weeks	Post-intervention questionnaires	Links via REDCap™
3.2	2 years & 3 months	+6 months	Booster video 3 message	Links via REDCap™
3.3	2 years & 9 months	+8 weeks	Post-intervention questionnaires	Links via REDCap™

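### Child-behavior items are scored as improved or not, but no child-behavior answer precedes the first arm-specific video, so an early benefit shrinks the odds ratio and can reverse it

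*Protocol*

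**What the plan says.** Section 9.4.3 gives one rule for behavior outcomes: "Each individual question will be dichotomized into improved vs. did not improve based on the answers given pre and post intervention". Single time points use logistic models. For the longitudinal analysis, "To evaluate behavioral changes over time, GEE models with a logit link function will be used". Results are reported as odds ratios.

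Behaviors toward the child are the target. Section 4.1 states: "Secondary outcomes will be changes in children's oral health behaviors conducive to better oral hygiene and dietary habits". Objective 2b in section 3 concerns mothers' changes in behaviors toward the child's oral health, and its endpoint reads: "behaviors toward the child's oral health will be assessed through a series of questions".

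The Schedule of Activities (section 1.3) places the arm-specific video at Visit 1, in pregnancy, and a booster at 3 months. The row "Child behavior questionnaire" is first ticked at the 9-month follow-up after Visit 1. It is then ticked at Visit 2, at the later 1- and 9-month follow-ups, and at Visits 3 and 4. The mother behavior questionnaire is ticked only at Visit 1 and at the first 1-month and 9-month follow-ups.

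Section 6.1.2 says: "Prior to watching the videotaped messages at visits 1, 2 and 3, participating women from both groups will complete a series of pre-intervention questionnaires". It lists the child's habits among the contents for all three visits, although the Schedule has no child-behavior form at Visit 1.

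**The concern.** A change code needs a starting answer that treatment has not touched. For child behaviors none exists: every scheduled answer follows randomization, video 1 and the sending of the first booster. Video 1 covers the needs of children aged 0 to 12 months, so it can affect these items directly.

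The protocol itself predicts an early effect. Section 4.1 says: "these hypothesized benefits will apply to both short-term (one-month) and long-term (nine-month) effects across each time point", and the prenatal time point is among those listed.

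The two-category code then works against the better arm. Mothers who adopted the behavior early and kept it are coded as not improved, together with mothers who never adopted it. If SDT works early, the SDT arm has more such mothers and fewer left who can improve. A named secondary outcome would be understated, or would point the wrong way, in the situation the trial hopes to find. If the same code served as the Objective 2b mediator, which the protocol does not state, the mediation result would inherit the problem.

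Mothers' own behaviors are not affected. The Visit 1 procedures run in the order "Enrollment, informed consent, group randomization, pre-intervention questionnaires, video 1 message", so those items have an answer from before the video, although it is listed after randomization.

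**Working it through.** **The plan's own figure.** The protocol states no rate, effect size or power for behavior items. Its 156 per group is for caries at three years and does not bear on this point. All rates below are assumptions.

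**Does the rule cover child items?** Section 9.4.3 speaks of maternal change in behavior and does not name the child questionnaire. Three facts tie them together:
- Objective 2b defines the maternal behaviors as those concerning the child.
- The mother questionnaire stops at the first 9-month follow-up, so from Visit 2 on the child questionnaire is the only scheduled behavior form (Visit 4 adds an intent form).
- Section 9.4.3 gives no other rule for behavior.

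**Model for a yes/no item.** Let p be the share favorable at the pre answer, t the later adoption among the rest, and r the relapse.
- Improved = (1 − p) × t
- Favorable afterwards = p(1 − r) + (1 − p) × t

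There is no relapse and no adjustment for the pre answer unless stated.

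**(a) Equal later adoption.** Control p = 0.50 and t = 0.40, so improved = 0.20 and favorable = 0.70. SDT has t = 0.40.

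| Early SDT gain | Improved, SDT | OR improved | Favorable, SDT | OR favorable |
|---|---|---|---|---|
| 0 | 0.20 | 1.00 | 0.70 | 1.00 |
| 5 points | 0.18 | 0.88 | 0.73 | 1.16 |
| 10 points | 0.16 | 0.76 | 0.76 | 1.36 |
| 15 points | 0.14 | 0.65 | 0.79 | 1.61 |

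Last row: (0.14/0.86)/(0.20/0.80) = 0.65 and (0.79/0.21)/(0.70/0.30) = 1.61.

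**(b) SDT also adopts faster later** (t = 0.50 against 0.40; control as in (a)).

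| Early SDT gain | Improved, SDT | OR improved | Favorable, SDT | OR favorable |
|---|---|---|---|---|
| 0 | 0.25 | 1.33 | 0.75 | 1.29 |
| 5 points | 0.225 | 1.16 | 0.775 | 1.48 |
| 10 points | 0.20 | 1.00 | 0.80 | 1.71 |
| 15 points | 0.175 | 0.85 | 0.825 | 2.02 |

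The sign turns at a gain of (1 − p_control) × (1 − t_control/t_SDT) = 0.5 × (1 − 0.4/0.5) = 0.10.

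**(c) Relapse of 10% in both arms, 15-point gain in (a).** Favorable is 0.65 × 0.9 + 0.14 = 0.725 against 0.50 × 0.9 + 0.20 = 0.65, OR 1.42. OR improved stays at 0.65.

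**(d) Control only 20% favorable at pre, 15-point gain.**
- Equal adoption of 40%: improved 0.26 against 0.32, OR 0.75; favorable 0.61 against 0.52, OR 1.44.
- SDT adoption 50%: improved 0.325 against 0.32, OR 1.02; favorable 0.675 against 0.52, OR 1.92. The turning point is 0.8 × 0.2 = 0.16.

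**Adjusting for the pre answer.** In (a), the odds ratio among mothers not favorable at pre is (0.4/0.6)/(0.4/0.6) = 1.0. The early gain is lost rather than reversed.

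**Graded items.** A simulated five-level item (1,000,000 per arm, within-person correlation 0.6) gave:

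| SDT effect | OR improved, exposed pre answer | OR improved, unexposed pre answer | OR for level |
|---|---|---|---|
| Early 0.4 SD, kept | 0.90 | 1.87 | 1.91 |
| Early 0.4 SD, then a further 0.2 SD | 1.19 | 2.49 | 2.64 |
| Early 0.4 SD, half fades | 0.67 | – | 1.38 |

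**The case against.** **The rule may be meant per video.** Section 6.1.2 places a pre-intervention questionnaire before each video, and each video has age-specific content. A Visit 2 answer is a valid starting point for the added change after video 2. This stands, but it measures the increment after video 2, not the effect of the assigned arm. Hygiene and diet recur across videos, and mothers already at the best answer are still coded as not improved.

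**Child items are not named in 9.4.3.** True. The link is an inference, though Objective 2b and the Schedule leave little room for another reading.

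**The reversals lean on assumptions.** Scenarios (a), (c) and the first part of (d) assume no later SDT advantage, whereas section 4.1 expects benefit at later time points too. With a later advantage of 50% against 40%, reversal needs an early gain above 10 points, or above 16 when control starts at 20%. Both arms see the same content in different styles, and nothing in the protocol supports gains of that size. This limits the claim of reversal; the attenuation remains.

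**Adjustment could help.** The covariates carried over from section 9.4.2 include mothers' behavior. If that means the pre answer, which is not stated, the reversal in (a) disappears, but so does the early benefit.

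**A statistical analysis plan could set the coding.** It could choose which answer is pre and how mothers at the best answer are handled. It cannot supply a child-behavior answer from before video 1.

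**Conclusion.** The concern holds. For child-behavior items, the scoring rule in section 9.4.3 relies on a pre answer that always follows the first arm-specific video. In every scenario examined, an early SDT gain lowered the odds ratio for improved; in some it fell below 1 while behavior was better in the SDT arm. Under the yes/no assumptions above, a 15-point early gain gives 0.65 to 1.02 for improved, against 1.42 to 2.02 for favorable behavior.

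The rates are assumed, so direction is firmer than size. With no early gain this distortion does not arise, and in the simulation graded items kept with a further gain were shrunk rather than reversed. The primary caries outcome and mothers' own behaviors are untouched. This should be changed, because it concerns a named secondary outcome and the remedy is cheap.

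**What to change.** In section 9.4.3, for child-behavior items only:
- Compare the behavior level (favorable yes/no, or the ordinal answer) between randomized arms at each scheduled time point from the first 9-month follow-up onward, using the logistic and logit GEE models already planned. Randomization makes this comparison valid without a baseline answer.
- Treat Visit 2 and Visit 3 child-behavior answers as outcomes, not as baselines or adjustment covariates.
- If child behavior is the Objective 2b mediator, use the same level variable.
- Keep change from Visit 1 for mothers' own behaviors. Child change scores from Visits 2 and 3 can be reported descriptively.
- Reconcile the section 6.1.2 list of pre-intervention content with the Schedule on what is asked about the child at Visit 1.

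The cost is a wording change and recoding of items already scheduled. The downside is that child results become behavior prevalence rather than percent improved, so the change in behavior named in Objective 2b is read, for these items, as a difference between arms.
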